Outcomes Assessment: The primary outcome measure is the worst pain in the prior 7-days (BPI SF-3). Secondary measures include pain interference with ADLs (BPI SF-9); QoL (SF-36); shoulder impairment (isometric voluntary abduction shoulder torque (IVAST), shoulder kinematic analysis, optional Fugl-Meyer Motor Assessment (upper limb)); and measures of central sensitization (mechanical pain thresholds for hyperalgesia, optional pinprick pain thresholds for hyperalgesia, temporal summation of repetitive pin-prick stimuli). Other optional measures include tactile/touch, vibration and thermal/thermal pain detection thresholds, temporal summation of repetitive thermal stimuli, and Conditioned Pain Modulation (CPM). Details for each measure are presented below. The outcomes are administered face-to-face in a blinded manner.

Brief Pain Inventory SF-3: The BPI has excellent psychometrics [86-92] and is recommended by the IMMPACT group for the assessment of pain in clinical trials. [75] The developers of the BPI recommend BPI SF-3, the "pain worst" rating, as the primary response metric. The question asks participants to rate their worst pain in the prior 7-d on a 0 to 10 NRS, where "0" indicates "No pain" and "10" indicates

“Pain as bad as you can imagine.” In order to gain a more comprehensive assessment of participants’ pain experience, daily least pain (BPI SF-4), daily average pain (BPI SF-5) and daily present pain (BPI SF-6) after morning ADLs are also collected. To analyze successful treatment, short-term responders will be defined as those who have a clinically meaningful 30% reduction of pain [72] at end of treatment. Long-term responders will be those who continue to have 30% reduction at weeks 8 and 12. The investigative team has extensive experience with the BPI. [2, 5, 8, 10, 11, 13, 70, 71, 93, 94]

Pain interference with ADLs – BPI SF-9: BPI SF-9 specifically evaluates the impact of pain on ADL performance within 7 domains of daily activity over a 7-day period: general activity, mood, walking ability, normal work, relations with other people, sleep and enjoyment of life on a 0-10 NRS, where 0 indicates “does not interfere” and 10 indicates “completely interferes.” [124] The BPI SF-9 score is the average of the scores for the 7 domains. Psychometrics have been evaluated as part of the BPI battery. [86-89] BPI SF-9 has been used to evaluate the impact of percutaneous PNS mediated pain reduction on ADLs. [6, 8, 11, 13, 62, 70]

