Visit 6 - EOT Outcomes Assessment & Explant Procedure: Study outcome measures administered (4 weeks post-Implant). PGIC administered. Skin checked, subject queried for medication usage and adverse events. Lead Removed. X-rays performed (may be done as separate clinical visit). (~4.5 hrs)

Phone Call #3 - 1 week Post-Explant Safety Check: Subject queried on condition of Lead exit site. (15 min)

Visit 7 - 8-wk Outcomes Assessment: Subset of study outcome measures

(questionnaires only) administered (8 weeks post-Implant (4 weeks post-EOT)).
Subject queried for medication usage. (~1 hr)

Visit 8 - 12-wk Outcomes Assessment: Subset of study outcome measures
(questionnaires only) administered (12 weeks post-Implant (8 weeks post-EOT)).
Subject queried for medication usage. (~1 hr)

Visit 9 - 16-wk Outcomes Assessment: Study outcome measures administered (16
weeks post-Implant (12 weeks post-EOT)). Subject queried for medication usage.
(~4 hrs)

Provision for lead replacement: If, in the judgement of the Investigator, the Sprint
MicroLead becomes significantly displaced or fully dislodged, it is possible that the
Investigator may elect to place another lead which would require an unscheduled
visit and additional 48-72 hour safety check. Other visits may be repeated as
appropriate.

Unscheduled Visits are conducted if/as needed.

8.7 Please attach study design/subject visit schedule here:

Name	Description
PNS Dose for HSP Visit Schedule Table (06-14-2017) History	

*If you have an
electronic schedule of study visits
and/or procedures please attach
here.*

View: 09-00 Inclusion/Exclusion Criteria

9.0 Inclusion/Exclusion Criteria:

9.1 What are the inclusion criteria? Put this information in bullet form:

- shoulder pain localized to the glenohumeral joint, subacromial area or deltoid insertion associated with: a) rest; b) passive abduction or external rotation range of motion (ROM); c) active abduction ROM; or, d) manual palpation;
- shoulder pain onset or worsening after the most recent stroke;
- weakness of shoulder abductors ($\leq 4/5$ on MRC if isolated movement is present);
- ≥ 21 -yrs old; < 90 -yrs old;
- time of stroke ≥ 3 -mo;
- duration of HSP ≥ 3 -mo;
- HSP with moderate to severe pain (BPI SF-3 ≥ 4);
- cognitive and communication ability to fulfill study requirements (cognitive ability based upon a score of ≥ 24 on the Mini Mental Status Exam (MMSE));
- availability of reliable adult who can assist with study procedures if necessary;

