- Collection of bloodwork (standard): The blood test (INR score) is standard for patients taking anticoagulants. This test will be collected in applicable subjects at Visit 1. A standard pregnancy test will also be administered in applicable subjects and can either be urine or serum pregnancy test.
- EMG needle electrode testing (experimental): EMG needles are commonly used to evaluate muscle physiology and strength of muscle contractions. In this study, however, EMG needle (Sprint Test Needle) testing will be used to deliver test stimulation during the lead implant procedure.
- Placement of Percutaneous Fine Wire Intramuscular Lead (experimental): The placement of the lead during the lead implant procedure and the use of stimulation during the treatment phase are experimental. Local anesthetic will be used.
- X-rays (standard): One 2-view (AP/Lateral and Scapular Y) shoulder x-ray will be conducted following the removal (explant) of the electrode lead, to determine and document the presence of any retained fragments.
- Collection of surveys and questionnaires - BPI, SF-36 (standard): These surveys are used for research, but are commonly used in pain patients. These surveys will be collected as defined elsewhere in this protocol for Outcomes Assessments Visits; the BPI additionally is collected at the Start of Stimulation Visit. The Mini Mental Status Exam (MMSE, also standard) will be collected at Visit 1. The BDI and PCS (also standard) are used for research, but are commonly used in pain patients. They will be collected at Visit 1. The FABQ (experimental) will be collected at Visit 1. The PGIC (experimental) will be collected at Visit 6.
- Fugl-Meyer Motor Assessment (upper limb): The FMA (standard) will be used as defined elsewhere in this protocol for Outcomes Assessments Visits.
- Other outcomes measures (experimental): Isometric voluntary abduction shoulder torque (IVAST), shoulder kinematic analysis, and measures of central sensitization (mechanical pain thresholds for hyperalgesia, pinprick pain thresholds for hyperalgesia, temporal summation of repetitive pin-prick stimuli) are used for research but some also are used in clinical practice as well. They will be used as defined elsewhere in this protocol for Outcomes Assessments Visits. Optional measures include tactile/touch, vibration and thermal/thermal pain detection thresholds, temporal summation of repetitive thermal stimuli, and Conditioned Pain

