Some participants may experience a vasovagal ("fainting") response due to the discomfort or anxiety associated with of the procedure, especially among those with prior history of "fainting." This risk is rare and may be associated with symptoms of lightheadedness, dizziness and or diaphoresis with concomitant reduction in blood pressure and heart rate. For those with prior history of "fainting" the procedure will be performed with the subject in the lateral decubitus position.

To minimize the risks associated with percutaneously placing fine wire leads, only appropriately trained physician investigators will perform the procedure. In addition, the risk of excessive bleeding will be reduced by excluding candidates who are taking warfarin with an INR > 3.0 and by placing manual pressure on the implantation site until hemostasis is achieved. Finally, the risk of discomfort during the procedure will be reduced by the use of an appropriate amount of local anesthetic.

It is possible that, in some cases, multiple attempts may be required to achieve appropriate placement of the Lead during the procedure. Each additional attempt at Lead placement carries the same risks as the initial attempt described in this section.

- 2) Risk of skin irritation, infection, or inflammation at the Sprint MicroLead exit site

There are risks of leaving a Sprint MicroLead in place for 4 weeks, including skin irritation, infection, and granuloma formation (mild tissue inflammation) at the Lead exit site. Symptoms include redness, swelling, or pain. The risk of skin irritation is common while the risks of infection and granuloma formation are rare.

These risks will be minimized by using sterile Leads and thoroughly

insertion. The insertion site will be covered with a dressing to keep it clean and dry, and the subjects and their caregivers will be instructed to inspect the site for signs of infection or irritation regularly and to inform the Investigator if they occur. If infection or skin irritation occurs, the Investigator will administer an antibiotic and/or remove the Lead. Infections are rare and typically resolve after Lead removal and antibiotic treatment.

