Subjects taking warfarin are at greater risk for developing bruises following venipuncture. However, the risk of discomfort and bruising at that puncture site will be reduced by applying gentle pressure following venipuncture as is the standard practice for collection of blood samples. The rare risk of infection due to venipuncture will be reduced by using proper blood collection technique including wiping the puncture site with an appropriate cleansing solution.

Some subjects may experience a vasovagal ("fainting") response due to the discomfort of needle insertion or anxiety associated with the procedure. The risk of fainting will be reduced by observing subjects during and following venipuncture to ensure that they feel comfortable rising from their seated position. Subjects with a history of vasovagal responses will be supine during venipuncture.

15) Risk of worsening of pain symptoms

It is possible that the subject may have a worsening of pain symptoms or that they may not obtain any therapeutic benefit from the treatment. The risk of worsening pain symptoms is uncommon. In addition, subjects will have the opportunity to discontinue treatment if their stimulation is too uncomfortable.

These risks are mitigated by clinical training on the safe limits. Subjects do not have access to make changes to the programming controls and thus could not advertently change the value.

16) Risks of Outcomes Assessments

The questionnaires and Fugl-Meyer Assessment present no risks. The assessments of shoulder torque and kinematics may be slightly uncomfortable. The measures of central sensitization (mechanical pain thresholds for hyperalgesia, pinprick pain thresholds for hyperalgesia, temporal summation of repetitive pin-prick stimuli) may be slightly uncomfortable and may cause brief skin irritation. The optional measures (tactile/touch, vibration and thermal/thermal pain detection thresholds, temporal summation of repetitive thermal stimuli, and Conditioned Pain Modulation (CPM)) also may be uncomfortable and may cause brief skin irritation.

17) Other

Some of the survey questions present a rare risk of psychological harm.

When PHI is involved there is the rare risk of a privacy breach.

There may be other risks as yet unknown.

10.6

Are there defined stopping rules? Yes No

Describe in enough detail for the IRB to assess safety.

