What are the stopping rules for the study? What are the conditions under which a subject will be withdrawn from the study for safety reasons, i.e. disease progression?

The study could be terminated at any time for valid scientific reasons or reasons related to the protection of subjects participating in this study. A reason for study termination includes but is not limited to the discovery of an unexpected, significant, or unacceptable risk to the participants enrolled in the study.

What findings, events, or conditions would require a research subject to be removed from the study? (i.e. disease progression)

The research subject may be removed if they develop any condition during the course of the study which would preclude the safe use of stimulation or otherwise impair their safe participation in any study activity.

10.7 **What Category of risk will study participants be exposed too?**

Name

Psychological

Physical

Privacy

Should be consistent with risks listed in the Consent Form.

10.8 **If Other listed above please specify:**

A text box is provided for further explanation.

Describe the availability of medical or psychological services that participants might require as a consequence of participation in this the research:

A text box is provided for further explanation.

10.9

It is not expected that participants would require medical or psychological services as a consequence of participation in this research. If that were to occur, appropriate referrals would be made for the subject.

10.10 **Describe in detail any measures in place to minimize or protect against the exposure of study subjects to these risks:**

1) Risks associated with needle insertion for Sprint MicroLead placement

To minimize the risks associated with percutaneously placing fine wire leads, only appropriately trained physician investigators will perform the procedure. In addition, the risk of excessive bleeding will be reduced by excluding candidates who are taking warfarin with an INR > 3.0 and by placing manual pressure on the implantation site until hemostasis is achieved. Finally, the risk of discomfort during the procedure will be reduced by the use of an appropriate amount of local anesthetic.

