21.5 Is this device intended as an implant? No *Check one*

21.6 Is device to be used in supporting or sustaining human life? No *Check one*

21.7 Is the device for use of substantial importance in diagnosing, curing, mitigating, or treating disease or otherwise preventing impairment of human health? *Check one*
No

21.8 Does this device present a potential for serious risk to the health, safety, or welfare of a subject? *Check one*
No

21.9 If you answered NO to all the above, or if an initial risk assessment has determined that this is a non-significant risk device (21CFR 812.3), attach the appropriate documentation for this justification: *Attach justification.*
Name Description
There are no items to display

21.10 What is the regulatory status of the study device? *Provide information on the*

FDA Cleared via 510(k) and used in accordance with its labeling (thus exempt from IDE regulation).

regulatory status of the device.

21.11 What is the long term plan for device management once the study closes?

Devices are not retained by subjects beyond the Treatment Phase.

Provide information such as how you will communicate important information to subject; plan for maintenance/repairs; contact information besides the PI.

View: 21-01 Medical Device Information II

21.1 Medical Device Information II:

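### The removal rule lets the investigator end a participant's follow-up for a condition that only rules out stimulation, although BPI SF-3 could still be collected safely

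*Protocol*

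**What the plan says.** Under stopping rules, the form in Section 10.6 asks "What findings, events, or conditions would require a research subject to be removed from the study". The protocol answers that the subject "may be removed if they develop any condition during the course of the study which would preclude the safe use of stimulation", and adds a second ground, joined by 'or': a condition that makes taking part in some study activity unsafe. Section 18.01 item 4.B carries the same question and answer, drawn from the same entry.

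On the outcome, Section 8.4 states: "The primary outcome measure is the worst pain in the prior 7-days (BPI SF-3"). Section 10.5 item 16 says: "The questionnaires and Fugl-Meyer Assessment present no risks"; item 17 adds only a rare risk of psychological harm from some survey questions. By Section 8.6, Visits 7 and 8 consist of questionnaires only, with a medication query.

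Elsewhere the protocol describes safety problems as matters for the device or the treatment. For infection or skin irritation, "the Investigator will administer an antibiotic and/or remove the Lead" (Section 10.5 item 2). Pregnancy leads to stopping stimulation and removing the lead (item 9), a scheduled MRI to removing the lead (item 12), and undue discomfort to the option of ending treatment (item 15). None of these items says whether outcome visits go on.

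**The concern.** The rule does not separate stopping treatment from leaving the study. Because its two grounds are alternatives, a condition that bars stimulation is enough for removal even if every remaining questionnaire could be completed safely. Real hazards in the assessments fall under the second ground, so the first adds no protection for data collection. It only permits follow-up to end.

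At stake are the BPI SF-3 scores from end of treatment onward and, with them, both responder classifications in Section 8.4, which depend on pain at end of treatment and later. An analysis plan can say how missing scores are handled, but it cannot recover scores that were never collected. The arms differ only in stimulation time (3, 6 or 9 hours a day), and Section 10.5 item 10 calls muscle fatigue unlikely with six hours without addressing nine. Stopping related to dose is therefore conceivable, and removal from the study would then make the missing scores related to dose as well. The protocol does not show that this would happen.

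**Working it through.** There is no figure in the protocol to reproduce on this point. The check sets the rule against the visit schedule and then sizes the loss.

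**Which BPI SF-3 ratings exist, and when**

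1. Up to the start of stimulation: the BPI is used for eligibility (Section 9.3), at baseline (Visit 2) and among the questionnaires at implant (Visit 3). For Visit 5, Section 10.1 notes that "the BPI additionally is collected at the Start of Stimulation Visit". All of these come before stimulation or at its start.
2. During the three weeks of stimulation: Section 8.6 schedules two phone calls that ask about pain, but no visit at which the BPI is listed.
3. From end of treatment: Visits 6, 7, 8 and 9, at 4, 8, 12 and 16 weeks after implant.

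A participant removed between Visits 5 and 6 therefore loses all 4 scheduled BPI SF-3 ratings that could show a treatment effect.

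**Size of the loss**

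Inputs: 30 participants and 3 doses (Section 8.4). Equal arms are an assumption: 30 / 3 = 10 per arm.

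- Assessments per arm from end of treatment onward: 10 × 4 = 40. One removal during treatment loses 4 / 40 = 10%.
- Standard error of a between-arm difference, relative to 10 against 10, with the same standard deviation in both arms:
  - one lost: √[(1/9 + 1/10) / (1/10 + 1/10)] = √(0.2111 / 0.2) = 1.027, a rise of 2.7%;
  - two lost in the same arm: √[(1/8 + 1/10) / (2/10)] = √(0.225 / 0.2) = 1.061, a rise of 6.1%.
- Shift in an arm mean when one score is lost that lies d points from the mean m of the other nine: the mean of all ten is (9m + m + d) / 10 = m + d/10, so the shift is d/10. The protocol gives no value for d. As an assumed range, d = 2 gives 0.2 points and d = 5 gives 0.5 points on the 0 to 10 scale.

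**Cost of keeping the participant**

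Visits 6 to 9 as planned take about 4.5 + 1 + 1 + 4 = 10.5 hours (Section 8.6). If Visits 6 and 9 are reduced to questionnaires, like Visits 7 and 8, the total is about 4 × 1 = 4 hours.

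**The case against.** The strongest reply is that the rule is permissive and was written in answer to a safety question. The words about removal from the study belong to the printed question, and item 4.B only repeats the entry. The investigator's sentence says 'may', so data are lost only if someone chooses to drop a participant who could have stayed. A reader might infer that stopping stimulation means stopping follow-up; the text does not say that, and the items on infection, pregnancy, MRI and discomfort point the other way. This stands as a limit on the concern. It does not remove it, because the answer takes its meaning from the question and no sentence in the text at hand keeps such a participant in follow-up. Attachments that are listed but not shown, such as the study termination form and the monitoring plan, might do so.

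A reader might also infer that the rule threatens data throughout the 12 weeks after explant, since it refers to the whole course of the study. That reading is too literal. The lead comes out at Visit 6, and Section 21.11 says "Devices are not retained by subjects beyond the Treatment Phase", so the stimulation ground then has nothing practical to act on. The clause is surplus wording in that period and should not be counted as a source of data loss.

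Nor would a participant removed during treatment lack all on-treatment pain data. Section 8.4 says that daily ratings on BPI SF-4 to SF-6 are also collected, without giving their timing, and the two phone calls ask about pain. The gap concerns BPI SF-3, which these sources do not replace.

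Finally, such removals are probably few. Section 10.5 rates exit-site infection as rare and stimulation discomfort as uncommon, and this is a pilot of 30. That bears on the weight of the point and not on whether the wording should be corrected.

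**Conclusion.** The point holds in a limited form. As written, the rule gives the investigator discretion to end study participation for a condition that only rules out stimulation, and so to forgo primary-outcome data that could be collected safely. One such removal during treatment costs all four BPI SF-3 ratings from end of treatment onward, 10% of an arm's total if arms are of 10, and raises the standard error of a between-arm difference by 2.7%. The number of participants affected is unknown and probably small. A claim of bias between doses would go beyond the documents, which give no removal rates by arm; the shift of 0.2 to 0.5 points rests wholly on an assumed distance of 2 to 5 points. The change is a cheap improvement: the gain may be modest, but little stands against it.

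**What to change.** In Section 10.6 and Section 18.01 item 4.B, make a condition that rules out safe stimulation a ground for stopping stimulation and removing the lead, and nothing more. State that the participant then stays in the study and completes BPI SF-3 and the other questionnaires at the scheduled weeks 4, 8, 12 and 16 after implant (Visits 6 to 9), including week 4 when the lead came out early. Physical tests that would be unsafe are left out, and the date of and reason for stopping are recorded. Follow-up ends only if consent is withdrawn or the participant cannot take part safely in the assessments.

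The cost is a short amendment to two places. It adds no visits: each affected participant attends at most four that are already scheduled, about 4 hours in all if only questionnaires are given and about 10.5 hours if Visits 6 and 9 are done in full.

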Investigators at the Cleveland FES Center and Case Western Reserve University have over 30 years of experience with dozens of research participants and hundreds of implanted leads like those used in this study. Infections and granulomas of leads or lead fragments have been uncommon, which is attributed to the materials and procedures that have been developed as well as the extensive experience of the Investigators.

5) Risks associated with lead fragment removal

Subjects will be instructed to contact the Investigator if there are any signs of pain, redness, swelling, discharge, or the appearance of a pimple-like mass (skin abscess). Such signs indicate that the fragment has migrated to the skin surface. At that time, if clinically warranted, the fragment may be removed via an outpatient procedure which involves lancing the abscess and removing the fragment and application of a topical antibiotic.

6) Risk of Lead Replacement due to Lead Migration or Lead Becoming Dislodged

It is possible that the Lead may migrate from its original intended location or that the Lead may become dislodged (i.e. come out completely) during the treatment phase. Each time an additional lead is placed, the subject has an additional exposure to the same risks of lead placement described above in "risk of needle insertion for Sprint Micro Lead placement".

This risk of lead migration or the becoming dislodged is mitigated by instructions to the subject and their caregiver, as appropriate, to ensure careful handling of the Lead and Lead Connector during bandage changes. In addition, the risk of placing a new lead is further mitigated by ensuring that Investigators are trained in the lead placement procedure, ensuring that the shoulder tissue appears healthy prior to placing a new lead, and collecting an additional INR blood sample for subjects who are taking warfarin.

7) Risk of skin irritation under the Sprint Pad or bandages

The risks of skin irritation under the Sprint Pad (a modified surface electrode) and under the bandages surrounding the Sprint MicroLead exit site will be reduced by excluding patients with known sensitivity to skin surface electrodes and/or medical-grade adhesive tapes. Subjects and their caregivers will be advised to examine the electrode exit site at regular intervals to look for any signs of irritation. To avoid irritation under the Sprint Pad, subjects will be advised that the Sprint Stimulator and Sprint Pad may be moved to slightly different locations near the Lead insertion site throughout the treatment phase. In addition, subjects will be instructed to avoid placing the Sprint Pad or bandages on unhealthy skin.

8) Risk of mechanical or electrical failure of the Sprint Stimulator

There is a rare chance that the Sprint Stimulator may malfunction. It is very unlikely that a stimulator malfunction will be harmful. If there is a problem with the Sprint Stimulator or the Sprint MicroLead, the Stimulator will reset itself such that no stimulation is delivered.

The Sprint Stimulator will not deliver stimulation if it detects a high impedance level

indicating a broken lead wire or a faulty lead connection. Subjects will be instructed to contact study staff in the event that an error message is displayed.

9) Risks for pregnant women

The risk of harm to a pregnant woman or fetus is unknown. The device will not be used in any subjects known to be pregnant. If a subject is known to become pregnant during the treatment phase, stimulation will be stopped and the Sprint MicroLead will be removed.

Potential risks of pregnancy will be reduced by administering a pregnancy test in females of reproductive potential at study enrollment. Additionally, the Informed Consent form will advise subjects that the risks of electrical stimulation during pregnancy are unknown and that they should immediately notify the Investigator if they suspect they have become pregnant during the study.

10) Risk of discomfort due to electrical stimulation

To minimize the risk of increased shoulder pain as the result of high intensity stimulation, the Investigator will set an appropriate intensity for the stimulation. Should a subject feel pain as the result of stimulation, he or she will be able to turn off the stimulation using the Sprint Stimulator controls. Although muscle fatigue is unlikely with six hours of daily stimulation therapy, subjects may also feel some discomfort if muscle fatigue occurs. If muscle fatigue is observed, the Investigator is able to prescribe several shorter stimulation sessions totaling six hours per day.

Discomfort or pain due to stimulation may occur if the Sprint MicroLead migrates from its original location. Stimulation near the skin surface may be perceived as a "pins and needles" or stinging sensation and may be uncomfortable.

The risk of pain due to a migrating electrode will be minimized by leaving stimulation off until the Sprint MicroLead has had time to stabilize. The Sprint MicroLead has a fine wire barb. In addition, the proximal portion of the Lead exits the skin which makes this Lead more susceptible to becoming dislodged during bandage changes. As a conservative measure, we allow one week for encapsulation of the Sprint MicroLead to ensure stability. Data on the Lead has shown that electrodes are fully encapsulated by the surrounding tissue.

A tingling sensation may be felt under the Sprint Pad but this sensation is not expected to be uncomfortable. If discomfort or pain is felt at the Sprint Pad site, the subject will be instructed to turn off stimulation and move the Sprint Pad and Stimulator to a different location.

11) Risks associated with Diathermy

The risk of diathermy will be reduced by informing subjects that diathermy must not be used. In addition, subjects will be informed to never undergo diathermy if a Sprint MicroLead fragment remains in the body.

12) Risks associated with MRI

Should a subject require a scheduled MRI during the treatment phase, the Sprint MicroLead will be removed. The decision to remove any remaining fragments will depend on a careful assessment of the benefits of the MRI, risks of MRI with retained fragments and risks associated with removing of electrode fragments.

13) Risk of allergic reaction to local anesthetics and/or risk of accidental injection of local anesthetic into a vein

The risks of allergy to local anesthetic agents will be reduced by excluding subjects with a prior known history of allergy or sensitivity to local anesthetic agents. In addition, prior to the procedure, subjects will be advised of the signs and symptoms of an allergic reaction. Because subjects will be awake during this procedure, they will be able to verbalize any itching or other signs of allergy to the local anesthetic. The risks of accidental intravascular injection of local anesthetic will be reduced by careful administration of the local anesthetic. Careful administration includes ensuring that a vein has not been punctured by the syringe prior to injecting the anesthetic and observing the subject after the injection. In addition, the physical location of the anesthetic injection (in the deltoid) combined with the injection technique would rarely result in an accidental intravascular injection.

14) Risk associated with venipuncture (if applicable)

Subjects taking warfarin are at greater risk for developing bruises following venipuncture. However, the risk of discomfort and bruising at that puncture site will be reduced by applying gentle pressure following venipuncture as is the standard practice for collection of blood samples. The rare risk of infection due to venipuncture will be reduced by using proper blood collection technique including wiping the puncture site with an appropriate cleansing solution.

Some subjects may experience a vasovagal (“fainting”) response due to the discomfort of needle insertion or anxiety associated with the procedure. The risk of fainting will be reduced by observing subjects during and following venipuncture to ensure that they feel comfortable rising from their seated position. Subjects with a history of vasovagal responses will be supine during venipuncture.

15) Risk of worsening of pain symptoms

It is possible that the subject may have a worsening of pain symptoms or that they may not obtain any therapeutic benefit from the treatment. The risk of worsening pain symptoms is uncommon. In addition, subjects will have the opportunity to discontinue treatment if their stimulation is too uncomfortable.

These risks are mitigated by clinical training on the safe limits. Subjects do not have access to make changes to the programming controls and thus could not advertently change the value.

16) Risks of Outcomes Assessments

If the subject feels discomfort, they may request that the outcomes assessments be paused. Measures will be taken to improve their comfort if possible. Skin irritation, should it occur, should resolved shortly after the cause is removed.

17) Other

Subjects may choose not to answer survey questions that make them uncomfortable.

Privacy breach precautions are included in Sections 15-17.

There may be other risks as yet unknown.

10.11 Please add any documents related to the above questions:

Name	Description
There are no items to display	

If your answers to the above questions are too long for the space provided please attach them here.

View: 10-02 Risk/Benefits

10.2 Benefits:

10.12 Describe the potential benefits to the subject as a result of participating in this research. If there is no direct benefit to subjects please state that as well: Note: payment or compensation to subjects for participation is not to be considered a potential benefit.

Participants may experience substantial pain reduction, and all subjects are receiving active treatment.

Describe potential benefits to the study subjects.

10.13 Describe the potential benefits to society as result of this research: The primary benefit will be the clinical and scientific knowledge gained.

Describe potential benefits to society.

